		suspected Fournier's gangrene. Study treatment interruption should be considered in patients with complicated UTI or with volume depletion (see Section 3.3.4 ).
Risks related to drug-drug interactions (DDI).	Pharmacokinetics and pharmacodynamics based DDIs	
Close monitoring of patients and the prohibited co-administration of impacted drugs such as treatment with a similar mechanism of action.
 
For further guidance, investigators are referred to the Investigator's Brochure [c01678844], Investigator Site File (ISF) or may contact the sponsor.

Table 1.4.2: 3      Overview of risks – trial procedures

Possible / known risks of clinical relevance	Summary of data, rationale for the risk	Mitigation strategy

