severe acute respiratory syndrome coronavirus 2 (SARS-CoV-2) or other severe infection	expected to have a relevant impact on the susceptibility to or the course of an infection. However, the underlying disease(s) of the patient population in this trial and the anticipated age of recruited patients does increase the risk of hospitalisation and intensive care in case of a SARS-CoV-2 or other severe infection	confirmed severe infection, trial treatment will be discontinued immediately and appropriate measures for monitoring, treatment and quarantine will be implemented. There are no trial-related restrictions regarding COVID-19 vaccination; patients can participate in the trial irrespective of their vaccination status, and vaccination during the trial is not restricted.  In the event of force majeure or other disruptive circumstances (e.g. pandemic, war) the investigational plan as per this CTP may not be feasible at a site. With the consent of the patient, the Sponsor and Investigator may agree on alternative, back-up or rescue methodology which may include, but will not be limited to, virtual patient visits and assessments, home healthcare nurse visits, and direct-to-patient shipments of trial medication. For full details refer to Section 6

A Hepatic Injury Adjudication Committee (AC) and Data Monitoring Committee (DMC) will be established to review safety data at regular intervals. For further details see [section 8.7](#).

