### 3.3.4.1 Discontinuation of trial treatment

Ideally, the patient should attend all remaining visits. Should the patient not agree, at least phone contacts should occur at the scheduled visit time points, should that not be acceptable, a phone contact once a year or at the end of the planned observation period should occur to collect the most relevant information: vital status (please see [section 5.2.6.2.1](#) ), outcome events, adverse events, or last contact date in case of lost to follow-up.

An individual patient will discontinue trial treatment (BI 685509 and empagliflozin) if:

- the patient wants to discontinue trial treatment. The patient will be asked to explain the reasons but has the right to refuse to answer.
- the patient has repeatedly shown to be non-compliant with important trial procedures and, in the opinion of both the investigator and sponsor representative, the safety of the patient cannot be guaranteed as he / she is not willing or able to adhere to the trial requirements in the future.
- the patient needs to take concomitant medication that interferes with the safety/efficacy of the investigational medicinal product or other trial treatment (refer to [Section 4.2.2.1](#)). If short-term, acute use of a restricted concomitant therapy is required (e.g. 5-7 days of antibiotic treatment for an infection), this will not automatically require discontinuation of BI 685509 or empagliflozin. Similarly, if a patient needs to modify a dose, where only a stable dose is permitted (e.g. NSBBs / carvedilol, statins, anti-viral therapy for HBV, pioglitazone, GLP1-agonists, or vitamin E), this also will not automatically require discontinuation. In both cases, the Sponsor should be consulted.
- the patient experiences a severe infection, e.g. with SARS-CoV-2, as determined by the Investigator
- the patient meets the criteria for hepatic injury (refer to [Section 5.2.6.1.4](#) and [Appendix 10.2](#))
- the patient has an acute liver decompensation event such as VH, new-onset of ascites, new-onset of overt encephalopathy, or other new-onset decompensation event based on Investigator judgement
- patients with worsening of their liver function (e.g. from Child-Turcotte-Pugh A to Child-Turcotte-Pugh B with clinical evidence of deteriorating liver function in the opinion of the Investigator). Refer to Child-Turcotte-Pugh classification method in [Appendix 10.3](#)

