- patients with a QT or QTcF interval > 500 ms, or an increase of QT or QTcF of > 60 ms from the pre-dose value at Visit 2 / enrolment (baseline). Such cases must be reported as AEs
- the patient can no longer receive trial medication for other medical reasons such as surgery, AEs, other diseases
- the patient has not successfully completed the dose titration period (i.e. Visit 4), but has persistent AEs or severe effects requiring down-titration of the trial medication (refer to [Section 4.1.4.1](#))
- a female patient becomes pregnant. The patient will be followed up until birth or otherwise termination of the pregnancy. The data of the patient will be collected and reported in the Clinical Trial Report (CTR) until last patient last visit and any events thereafter will be reported in the BI Pharmacovigilance (PV) database (refer to [Section 5.2.6.2.3](#))

Trial-specific procedures have also been defined for Investigators to follow in case of increased liver enzymes (AST, ALT, and total bilirubin) after enrolment. For details refer to [Section 5.2.6.1.4](#) and [Appendix 10.2 \(P09-12413\)](#).

In the event of intolerance to BI 685509 after successful completion of the dose titration period at Visit 4 (e.g. persistent AEs despite two down-titrations, or severe effects at any dose), permanent treatment discontinuation should also be considered, based on Investigator judgement (refer to [Section 4.1.4.1](#)).

In addition to these criteria, the Investigator may discontinue patients at any time based on clinical judgement.

If a patient permanently discontinues the trial medications before the last allocated dose, an Early Discontinuation (ED) visit is required ideally within 7 days of discontinuing the medication. An EoS visit should be performed 4 weeks after the ED visit. Refer to Sections [6.2.2.1](#) and [6.2.3](#) for further details, including guidance with respect to trial assessments that should be included as part of an ED visit.

An individual patient will permanently discontinue empagliflozin if:

- Ketoacidosis is suspected.
- Fournier's gangrene is suspected.

If a patient in treatment arm 4 permanently discontinues empagliflozin or BI 685509, the patient must permanently stop the treatment with the other trial medication as well.

In the following cases, empagliflozin must be interrupted:

- Complicated UTI, including urosepsis
- Symptomatic volume depletion

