##### **6.2.2.1 End of treatment / Early discontinuation visit**

Patients who successfully complete the entire 8 week treatment period should have the assessments for the EoT visit performed as indicated in the [Flow Chart](#). Such patients should

be registered as completed in the IRT system. End of trial medication must also be recorded on the corresponding eCRF.

For patients who discontinue trial medication prematurely (for whatever reason), an ED visit (refer to the [Flow Chart](#)) should be completed instead of the planned treatment period visit (refer to [Section 3.3.4](#)). Ideally the ED visit should be performed within seven days of discontinuing the trial medication. The assessments performed at the ED visit should be in accordance with the Flow Chart, with the following exceptions:

- HVPG: not required
- [REDACTED]
- biobanking sampling: not required

Patients who discontinue treatment early should be registered as discontinued in the IRT system. End of trial medication must also be recorded on the corresponding eCRF.

At the EoT and / or ED visit, patients should be reminded about restrictions (refer to [Section 4.2.2](#)) that still need to be observed up until the EoS visit (refer to [Section 6.2.3](#)). Home BP and HR monitoring should continue between the EoT / ED visit and the EoS visit.

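### For complicated UTI or urosepsis in treatment group 4, three unreconciled stop-or-interrupt instructions can apply; for volume depletion, two differ

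*Protocol*

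**What the plan says.** Four places in the protocol carry an instruction.

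- **Section 3.3.4.1, reasons for stopping.** The list opens "An individual patient will discontinue trial treatment (BI 685509 and empagliflozin) if" and includes "the patient experiences a severe infection, e.g. with SARS-CoV-2, as determined by the Investigator". It names neither UTI nor volume depletion.
- **Table 1.4.2:4**, in the row on SARS-CoV-2 or other severe infection: "confirmed severe infection, trial treatment will be discontinued immediately".
- **Section 3.3.4.1, further down.** "In the following cases, empagliflozin must be interrupted", followed by two entries: "Complicated UTI, including urosepsis" and "Symptomatic volume depletion". BI 685509 is not mentioned. The rule that ties the two drugs together in group 4 is triggered by permanent discontinuation of either, not by interruption. After a temporary stop, either or both drugs may be restarted where there is medical justification.
- **Table 1.4.2:2**, among the empagliflozin risks: "Study treatment interruption should be considered in patients with complicated UTI or with volume depletion", with a pointer to Section 3.3.4.

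For the endpoint, Section 6.2.2.1 sends a patient who stops early to an early discontinuation (ED) visit with "HVPG: not required". SAP Section 7.4.1 analyses on-treatment HVPG only. SAP Section 6.1 and Table 6.7:1 extend on-treatment to 8 days after the last intake, and SAP Section 6.6.1 imputes nothing.

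**The concern.** Complicated UTI (urosepsis named) and volume depletion are listed in Table 1.4.2:2 as risks of empagliflozin, so these are foreseeable events in the combination arm. A site should find one instruction for each. Instead, the passages differ on whether action is obligatory, which product it covers and, for urosepsis, whether it is a pause or a stop. Section 3.3 plans about 42 sites with about 2 patients each. Few sites would meet such an event twice, so handling may follow whichever passage is read first.

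The first thing at stake is consistency of a safety instruction. The second is the primary endpoint, because a patient who stops for good and a patient who pauses and resumes take different routes to Week 8.

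**Working it through.** **Instructions side by side (group 4)**

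| Event | Obligation | Product | Kind of stop | Source |
|---|---|---|---|---|
| Complicated UTI, urosepsis included | mandatory | empagliflozin | interruption | Section 3.3.4.1 |
| Complicated UTI | to be considered | study treatment | interruption | Table 1.4.2:2 |
| Urosepsis, if judged a severe infection | mandatory | both drugs | discontinuation | Section 3.3.4.1, Table 1.4.2:4 |
| Volume depletion, if symptomatic | mandatory | empagliflozin | interruption | Section 3.3.4.1 |
| Volume depletion, unqualified | to be considered | study treatment | interruption | Table 1.4.2:2 |

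That is three instructions for complicated UTI or urosepsis and two for volume depletion. No passage ranks them, even though two of the three for urosepsis stand in the same section. The stop list does not use the word permanent. That reading follows from its contrast with the temporary discontinuation described later in Section 3.3.4.1 and from the ED visit it leads to.

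**Which instruction affects the Week 8 HVPG**

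1. Mandatory versus considered interruption does not in itself decide whether a Week 8 value exists. A patient who pauses and resumes stays on course for the end-of-treatment measurement.
2. Permanent discontinuation of both drugs leads to the ED visit, where HVPG is not required.
3. A later measurement would rarely count. SAP Table 6.7:2 starts the extended Week 8 window at Day 51, and on-treatment status ends 8 days after the last intake. The last intake must therefore fall on Day 43 or later (51 − 8 = 43).
4. Nothing is imputed, so a patient stopped earlier has no value in the primary ANCOVA.

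Only urosepsis judged a severe infection takes this route. There is one smaller link. SAP Section 7.4.4 repeats the primary analysis without patients who had a dose interruption and does not say of which product. Whether a pause occurs can therefore change membership of that supplementary analysis, for volume depletion too.

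**Size**

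The point rests on no planned figure. For scale, Table 7.5:1 can be reproduced with a normal approximation, SD 25% and n = 20:

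P(observed mean reduction ≥ 10%) = Φ((μ − 10) / (25/√n))

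| True mean reduction μ | Table 7.5:1 | Recomputed, n = 20 |
|---|---|---|
| 20% | 96.3% | 96.3% |
| 15% | 82% | 81.4% |
| 5% | 18.8% | 18.6% |
| 0% | 3.8% | 3.7% |

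The documents give no event rate. Assuming, for illustration, that 0, 1 or 2 group 4 values are lost, with μ = 20%:

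- n = 20: Φ(10 / (25/√20)) = 96.3%
- n = 19: Φ(10 / (25/√19)) = 95.9%
- n = 18: Φ(10 / (25/√18)) = 95.5%

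**The case against.** The strongest reply is that the rules are tiered. Any complicated UTI pauses empagliflozin, and an infection the investigator judges severe stops both drugs. Stopping both also satisfies the pause, and restarting is conditional. Table 1.4.2:2 is a benefit-risk summary that points to Section 3.3.4, so a site that follows the pointer arrives at the mandatory rule. The trial is estimation-only, an HVPG at the ED visit is not forbidden, and Section 3.3.4 already requires the discontinuation decision and its reason to be recorded.

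Much of this stands. The severe-infection rule is conditional and does not name urosepsis, so it overlaps with the interruption rule rather than contradicting it in every case. The pointer weakens the reading that nothing is obligatory.

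Two things remain. The tiering is not written down, and the interruption list expressly places urosepsis, the serious end of UTI, among the events that lead to a pause. The pointer also does not remove the difference in obligation, product and trigger between Table 1.4.2:2 and Section 3.3.4.1.

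**Conclusion.** The wording needs reconciling. In group 4, three instructions can apply to complicated UTI or urosepsis, and two differ for volume depletion. The third for urosepsis depends on the investigator judging the infection severe. The primary endpoint is touched only where that judgement leads to a permanent stop of both drugs, and usually only if the last intake is before Day 43. On the assumed loss of one or two values, the planning probability falls by less than 1 percentage point (96.3% − 95.5% = 0.8). The case for change is clarity of a safety instruction, not precision.

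Three stronger readings may tempt a reader, and the documents do not support them:

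- *Volume depletion also carries a stop-both-drugs instruction.* No passage names it as a reason. Only the general clauses on adverse events, other medical reasons and clinical judgement could lead there, and those apply to any event.
- *The same urosepsis would be lost in group 3 and kept in group 4.* The severe-infection rule covers every group. Groups 1 to 3 can also be interrupted and restarted for a possibly related adverse event (Sections 4.1.4 and 4.1.4.2). A difference by arm would need investigators to apply the shared rule unevenly, which no passage directs.
- *Empagliflozin is paused while BI 685509 must continue.* Section 3.3.4.1 is silent on BI 685509, and Section 4.1.4 allows trial medication to be interrupted.

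**What to change.** Reconcile Section 3.3.4.1 (the stop list and the interruption list) with Tables 1.4.2:2 and 1.4.2:4, so that complicated UTI or urosepsis and volume depletion each lead to one instruction. Each should name the product or products, say whether the stop is temporary or permanent, and use the same trigger throughout, including whether volume depletion must be symptomatic. One sentence should state how the severe-infection rule relates to the urosepsis rule. Which clinical rule applies is for the sponsor to decide; the review takes no position on it.

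The cost is a wording change in one section and two tables at the next amendment, with a letter to sites. It needs no extra patients, procedures or data items, since the decision to discontinue and its reason are already recorded under Section 3.3.4.

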### **3.3.4.2      Withdrawal of consent to trial participation**

Patients may withdraw their consent to trial participation at any time without the need to justify the decision.

If a patient wants to withdraw consent, the investigator should be involved in the discussion with the patient and explain the difference between trial treatment discontinuation and withdrawal of consent to trial participation, as well as explain the options for continued follow-up after trial treatment discontinuation, please see [Section 3.3.4.1](#) above.

If a patient withdraws consent for further trial participation, no further data will be collected from the respective patient.

Reporting of data of patients who discontinue/withdraw after randomization/entering the active treatment phase is described in [Section 7.2.1](#).

### 3.3.4.3 Discontinuation of the trial by the sponsor

Boehringer Ingelheim reserves the right to discontinue the trial overall or at a particular trial site at any time for the following reasons:

1. Failure to meet expected enrolment goals overall or at a particular trial site.
2. New efficacy or safety information invalidating the earlier positive benefit-risk-assessment (e.g. following a recommendation by the DMC), please see [Section 3.3.4.1](#).
3. Deviations from GCP, the trial protocol, or the contract impairing the appropriate conduct of the trial.

Further treatment and follow up of patients affected will occur as described in sections [3.3.4.1](#), [6.2.2.1](#) and [6.2.3](#).

The investigator / the trial site will be reimbursed for reasonable expenses incurred in case of trial termination (except in case of the third reason).

## **4. TREATMENTS**

### **4.1 INVESTIGATIONAL TREATMENT**

The investigational medicinal products in the trial are BI 685509 and empagliflozin. BI will supply all products.

#### **4.1.1 Identity of the Investigational Medicinal Products**

The characteristics of the investigational medicinal products are described in Tables [4.1.1: 1](#) to [4.1.1: 4](#) below.

Table 4.1.1: 1

BI 685509

Substance:	BI 685509
Pharmaceutical formulation:	Film-coated tablet
Source:	Boehringer Ingelheim Pharma GmbH & Co. KG
Unit strength:	
Posology:	BID
Method and route of administration:	Oral

Table 4.1.1: 2

BI 685509

Substance:	BI 685509
Pharmaceutical formulation:	Film-coated tablet
Source:	Boehringer Ingelheim Pharma GmbH & Co. KG
Unit strength:	
Posology:	BID
Method and route of administration:	Oral

Table 4.1.1:3

BI 685509

Substance:	BI 685509
Pharmaceutical formulation:	Film-coated tablet
Source:	Boehringer Ingelheim Pharma GmbH & Co. KG
Unit strength:	
Posology:	BID
Method and route of administration:	Oral

Table 4.1.1: 4

Empagliflozin 10 mg

Substance:	Empagliflozin
Pharmaceutical formulation:	Film-coated tablet
Source:	Boehringer Ingelheim Pharma GmbH & Co. KG
Unit strength:	10 mg
Posology:	QD
Method and route of administration:	Oral

#### 4.1.2 Selection of doses in the trial and dose modifications

BI 685509 has been tested in a single rising dose trial, a food effect and DDI trial and two MRD trials in male healthy volunteers. Single doses ranged from [REDACTED] to 5.0 mg and multiple doses up to [REDACTED] daily were tested. Overall, BI 685509 was well tolerated except for dose-limiting orthostatic dysregulation. Up-titration and 3 times daily dosing markedly improved the cardiovascular tolerability (refer to the IB [[c02778238](#)]).

One multiple oral rising dose trial in patients with DN has also been completed. Multiple oral doses up to [REDACTED] *TID* were found to be safe and well tolerated. The highest total daily dose of [REDACTED] was achieved following up-titration in 2 steps over 14 days.

An estimated human dose of [REDACTED] *BID* is predicted to achieve pharmacologically relevant exposure in patients with hepatic impairment [[c02778238](#), [n00261471-01](#)]. As [REDACTED] is the maximum tolerated single dose, 2 doses [REDACTED] *BID* and [REDACTED] *BID*) will be evaluated in the phase II trial 1366-0021, that is conducted in parallel in patients with CSPH in compensated alcohol-related cirrhosis. These doses have been selected based on safety and preliminary PK results from the ongoing Phase I MRD hepatic impairment trial (1366-0020).

In this trial, [REDACTED] BI 685509 *BID* maintenance dose and one arm [REDACTED] BI 685509 *BID* on top of 10 mg empagliflozin *QD* will be evaluated in the 3 different patient groups, with the potential to down-titrate, if not tolerated. The dose of 10mg empagliflozin *QD* was selected based on the dose used in the ongoing phase III empagliflozin in CKD trial (BI 1245-0137) [[c01678844](#)].

#### 4.1.3 Method of assigning patients to treatment groups

After the assessment of all in- and exclusion criteria, each eligible patient will enter the treatment phase at visit 2. HBV patients will be assigned to treatment group 1 and HCV patients to treatment group 2 via an Interactive Response Technology (IRT) system. NASH patients with T2DM will be randomised to treatment group 3 or 4 in a 1:1 ratio via the IRT system. NASH patients without diagnosis of T2DM will only be assigned to treatment group 3 via IRT. Refer to [Section 7.4](#) for further details regarding randomisation and access to the randomisation code.

Note that the medication numbers, assigned via the IRT system at each dispensing visit, are different from the patient number (which is generated via the IRT system when a new patient is registered [screened] in the system).

The Investigator (and relevant designated site personnel) will be provided with instructions to access the IRT system. The medication list is unblinded.

#### 4.1.4 Drug assignment and administration of doses for each patient

Trial medication will be dispensed at the investigational sites in accordance with the [Flow Chart](#). At dispensing visits patients will be given the appropriate number of medication kits for BI 685509 (range 1-2) and empagliflozin (range 1-2) depending on the interval between the visits (for further kit details refer to [Section 4.1.6](#)). The last dose of BI 685509 will be administered in the evening of the day before the EoT visit and the last dose of empagliflozin in the morning of the day before the EoT visit.

All patients will start on a dose of [REDACTED] BI 685509 *BID* at Visit 2. Treatment group 4 will receive a fixed dose of 10mg empagliflozin *QD* in addition. 7 days later, at Visit 3, and again at Visit 4, 7 days after Visit 3, all patients will be up-titrated to a dose of [REDACTED] BI 685509 *BID*, and then to the maintenance dose of [REDACTED] BI 685509 *BID*.

Patients will be informed of the dose titration period and will be made aware that up-titration for BI 685509 is being used. If a patient does not tolerate an up-titration, e.g. due to orthostatic dysregulation, the rules in [Section 4.1.4.1](#) must be followed. From Visit 4 onwards, patients of the treatment group 1, 2, 3 and 4 will continue to receive the maximum dose of [REDACTED] BI 685509 (plus 10mg empagliflozin *QD* for group 4 only) until reaching the EoT visit (8 weeks after starting the trial medication).

If a patient has an AE that, based on Investigator judgement, may be related to BI 685509 or empagliflozin, the trial medication can either be:

- interrupted (i.e. the trial medication is stopped, and subsequently re-started. The up-titration approach described above is followed.)

OR

- the dose can be reduced (down-titrated) for BI 685509 if the patient has successfully completed the dose titration period (i.e. Visit 4). No dose reduction is allowed for empagliflozin.

For further details refer to Sections [4.1.4.1](#) and [4.1.4.2](#).

All trial medication assignments, including up / down-titrations for BI 685509 and provision of replacement kits, will be managed through the IRT system. Down-titrations of BI 685509 must not be performed by instructing the patient to take less than the two daily doses (refer to [Section 4.1.4.1](#)).

Table 4.1.4: 1 Drug assignment and dosage by treatment group

Randomisation Allocation	Week 1 of Treatment	Week 2 of Treatment	Week 3 of Treatment Onwards
	Dispensed at Visit 2	Dispensed at Visit 3	Dispensed at Visit 4 onwards
Treatment group 1, 2 and 3 (BI 685509 [REDACTED] BID)	[REDACTED] BI 685509	[REDACTED] BI 685509 (Up-titration)	[REDACTED] BI 685509 (Up-titration)
Treatment group 4 (BI 685509 [REDACTED] BID + Empagliflozin 10mg QD)	[REDACTED] BI 685509 + 10mg Empagliflozin	[REDACTED] BI 685509 (Up-titration) + 10mg Empagliflozin	[REDACTED] BI 685509 (Up-titration) + 10mg Empagliflozin

From the start of the treatment period (i.e. from Visit 2), and until reaching the EoT visit 8 weeks later, patients will be instructed to take BI 685509 orally twice a day (BID) and empagliflozin orally once a day (QD).

Each dose of BI 685509 will consist of one film-coated tablet. It is recommended that the first daily dose is taken in the morning, and the second dose in the evening. Ideally there should be at least 10 hours in between the intake of each dose. BI 685509 should be taken at approximately the same time every day. If a dose is missed this must not be rectified by taking two doses (i.e. double doses) at the next time point; if a dose is missed by more than 6 hours, that dose should be skipped altogether and the next dose taken as scheduled. Also refer to [Section 4.1.4.2](#) for further details regarding interruption of trial medication. Trial medication should be taken with a glass of water and can be taken with or without food.

Patients in the treatment group 4 will be taking in addition one film-coated tablet of empagliflozin together with the first daily dose of BI 685509 in the morning. To ensure a dose interval of about 24 hours for empagliflozin the medication should be taken in the morning approximately the same time every day. If a dose of empagliflozin is missed by more than 12 hours, that dose should be skipped and the next dose should be taken as scheduled. No double doses should be taken. Both medications should be taken together with a glass of water and can be taken with or without food.

In the morning of a visit, the trial medication will be administered as part of the visit. Therefore, on these days, patients should be instructed not to take their morning dose in advance of the visits. [REDACTED]

Patients who fail to follow these instructions should have the visit re-scheduled as soon as possible, ideally on the following day (refer to [Section 6.1](#)). On days with no scheduled visit the patient will self-administer their medication at home. Patients should be instructed to bring all unused trial medication and empty wallets / packaging with them when they return for clinic visits to the investigational site.

In case of a temporary interruption to treatment, refer to Sections [3.3.4.1](#), [4.1.4.1](#) and [4.1.4.2](#).

In the event of force majeure or other disrupting circumstances (e.g. pandemic, war; refer to [Section 6](#)) physical patient visits to sites may not be feasible or may need to be restricted to ensure patient safety. Based on a thorough assessment of the benefits and risks, the Investigator may still decide to continue trial medication, and, if acceptable according to local law and regulations, trial medication may be shipped from the site to the patient's home.

